9.4.1 Pharmacokinetic Parameters

The plasma concentrations of SNF472 obtained at predose and at the end of the infusion time (EOI) will be reported. EOI corresponds to the maximum (peak) plasma concentration during the dosing interval (C_{max}), based on data from previous clinical studies. Standard pharmacokinetic parameters will not be calculated due to the lack of experimental points in the plasma concentration-time profile of SNF472.

Descriptive statistics of the pharmacokinetic parameters will be presented by visit and timepoint and will contain the following information:

-
- SNF472 dose: expressed in mg
 - T_{inf} : actual infusion time. Expressed in minutes
 - Actual sampling time: actual sampling time. Expressed in minutes
 - Pre-dose plasma levels: expressed in ng/mL or as below of the lower limit of quantification (BLQ).
 - End of infusion plasma levels (C_{max}): expressed in ng/mL

Individual data will be flagged for exclusion if actual time differs significantly from scheduled time. In those cases when the actual infusion time and actual sampling time at the end of the infusion differs significantly from the protocol time will be excluded from statistics, based on the pharmacokinetic criteria.

PK data will be listed by subject, visit and time-point. In addition, the same information listed using all time-points will be reported in a figure (Shell F-2).

On a case by case basis, it may be necessary to exclude individual infusion time values and concentration values because they are erroneous or abnormal. Any excluded data should be flagged in the individual data listings and the reason for exclusion should also be documented. If the exclusion has a meaningful impact on the overall interpretation of the results, then it should be discussed. Planned infusion and sampling times may be used as a replacement for unknown or missing actual times, based on the pharmacokinetic criteria.

9.4.2 Accumulation

Given the short half-life of SNF472, no accumulation of SNF472 plasma concentration is expected. Accumulation effects from Week 1 to Week 12 will be assessed on the C_{max} by comparing the difference between the two visits. Accumulation will be declared if the 90% CI of the difference does not include the value 0.

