Sodium phytate is also used for Technetium bone scanning (Fyton; 15 mg Na-phytate [31]). The dose prescribed varies from a minimum of 2.5 mg to a maximum 5.0 mg of 99mTc-phytate. This combination is used in medicine as a source of radiation for radiotherapy and for diagnostic purposes. Published data shows two half-lives:  $t_{1/2} \alpha$ : 2.4-7.0 min,  $t_{1/2} \beta$ : 69-105 min, with a distribution into bone and liver, and slow disappearance from liver. It is possible that this reflects the half-life of IP6 in humans.

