### **8.2.3. Treatment Period W1-W12**

All eligible patients will receive SNF472 during their haemodialysis sessions. SNF472 will be administered at each dialysis session for the entire duration of the study. The duration of infusion of SNF472 will range from 2.5 h up to maximum time on dialysis, which would be 4 h. SNF472 should NOT be administered directly intravenously. SNF472 should NOT be administered concomitantly with STS, should STS be used. In case both drugs would be administered to the patient, the administration of SNF472 should be stopped 30 minutes before the end of the dialysis session to allow the STS infusion to take place in the last 30 minutes of the session.

In the event of Fe+ administration, the infusion of SNF472 should be stopped BEFORE starting the Fe+ infusion.

For other assessments please check Table 1.

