9.4 Pharmacokinetics

The PK analysis will be summarized, listed and printed for the PK analysis set.

Plasma samples collected, at Week 1 and Week 12, pre and end of infusion will be used for PK assessment. The end of the infusion is the approximate time of C_{max}.

All concentration values below the LLQ and samples with no reportable value occurring prior to dosing will be replaced by "0". For tabulation, graphical representation and calculation purposes, all samples LLQ or with no reportable value observed after the drug administration will be set to missing.

Blood samples for the quantitation by LC-MS/MS of SNF472 will be taken on 2 different days at pre-dose and at the end of the infusion time on day 1 (Week 1), and on Week 12. Infusion should be performed during 2.5 to 4 hours at constant rate. The following parameters will be calculated:

- **Actual infusion time (T_{inf})** will be calculated as the difference between the actual clock time of the end of infusion time (EOI) and the actual clock time of the start of the infusion (SOI), i.e., T_{inf} = EOI - SOI. The actual infusion time will be expressed in minutes.
- **Actual sampling time** will be calculated as the difference between the sample collection actual clock time and the clock time of dosing starts. The actual sampling times will be expressed in minutes.

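### SAP 9.4.2 declares accumulation from unadjusted Cmax, so a net shift in infusion length, or even a fall in Cmax, can be called accumulation, while the Week 12 pre-dose level stays outside the rule

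*SAP*

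**What the plan says.** SAP 9.4.2 starts from the expectation that there will be none: "Given the short half-life of SNF472, no accumulation of SNF472 plasma concentration is expected". It then assesses accumulation on Cmax "by comparing the difference between the two visits" and gives a formal rule: "Accumulation will be declared if the 90% CI of the difference does not include the value 0". It states no log scale, ratio, or adjustment for infusion time.

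SAP 9.4 allows a range of infusion lengths: "Infusion should be performed during 2.5 to 4 hours at constant rate". Protocol 8.2.3 agrees: "The duration of infusion of SNF472 will range from 2.5 h up to maximum time on dialysis, which would be 4 h". Neither asks for the same length at both PK visits. Protocol 6.1 fixes the mg dose by dry body weight at Screening, so within a patient the rate varies inversely with the infusion length.

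SAP 9.4.1 excludes data when the actual infusion and sampling times differ significantly from the protocol time, with no threshold. It also summarises dose, actual infusion time (Tinf), sampling time, pre-dose level and end-of-infusion level by visit.

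SAP 9.4 says that, along with concentrations below the LLQ, "samples with no reportable value occurring prior to dosing will be replaced by" zero. Values below the LLQ or not reportable after drug administration are set to missing.

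**The concern.** For the same dose, a faster infusion gives a higher concentration at its end. A Week 12 minus Week 1 difference in Cmax therefore mixes carry-over with any change in infusion length, and the rule cannot separate them. The exclusion in SAP 9.4.1 does not clearly help: the protocol time is itself a range, so 2.5 h at one visit and 4 h at the other both comply.

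Two further weaknesses lie in the wording. A CI wholly below 0 excludes 0, so a fall in Cmax would be reported as accumulation. And drug still present before the Week 12 infusion would show carry-over whatever the infusion length, yet that level does not enter the rule. If a Week 12 pre-dose sample with no reportable value is entered as 0, the pre-dose summary is biased towards no carry-over.

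At stake is the correctness of a formal PK verdict over 12 weeks of dosing, when the repeat-dose experience described in Protocol 2.3.2 and 6.2 runs to about one month.

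**Working it through.** The plan gives no operating figure for this rule, so there is none to reproduce.

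**Inputs from the documents**
- Infusion length T: 150 to 240 min (SAP 9.4; Protocol 8.2.3).
- Same mg dose at both visits (Protocol 6.1).
- Terminal half-life 69 to 105 min, from labelled phytate (Protocol 2.1.2), which says only "It is possible that this reflects the half-life of IP6 in humans".
- Planned number of patients: 15 (SAP 6.4).

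**Assumptions not in the documents**
- One-compartment kinetics with constant-rate infusion.
- Within-patient CV of 15% to 40%; between-patient SD of 0.3 on the log scale.

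**Step 1. Effect of infusion length on Cmax.** For a fixed dose, Cmax is proportional to f(T) = (1 − exp(−kT))/(kT), with k = ln 2 / half-life.

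| Half-life | f(150) | f(210) | f(240) | 2.5 h vs 4 h | 3.5 h vs 4 h |
|---|---|---|---|---|---|
| 69 min | 0.5166 | 0.4165 | 0.3776 | 1.37 | 1.10 |
| 87 min | 0.5835 | 0.4855 | 0.4457 | 1.31 | 1.09 |
| 105 min | 0.6347 | 0.5410 | 0.5017 | 1.27 | 1.08 |

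The limit for a very short half-life is 240/150 = 1.6. At an assumed 300 min the 2.5 h to 4 h ratio is still 1.10. The size depends on the half-life; the direction does not.

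**Step 2. What the rule does when there is no accumulation.** Simulation of a paired difference in Cmax with a 90% t interval, 20,000 trials per setting. The first two rows and the last use n = 15, CV 20% to 40% and ratios 1.26 to 1.36; the two middle rows use n = 12, CV 25% to 15% and an 87 min half-life.

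| Change in infusion length, Week 1 to Week 12 | CI wholly above 0 |
|---|---|
| None, or balanced in both directions | about 5% (and about 5% wholly below 0) |
| Half the patients go from 4 h to 2.5 h | 40–55% (CV 20%), 25–36% (CV 30%), 18–25% (CV 40%) |
| All go from 4 h to 3.5 h | 19% to 36% |
| All go from 4 h to 3 h | 47% to 83% |
| All go from 4 h to 2.5 h | 90–98% (CV 20%), 62–83% (CV 30%), 43–62% (CV 40%) |

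If all go from 2.5 h to 4 h, the CI lies wholly *below* 0 about as often as in the last row. As worded, the rule calls that accumulation too.

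**Step 3. What the pre-dose sample would show.** With sessions 48 h apart and a 4 h infusion, 44 h remain. The fraction left is 2^(−2640/half-life) = 3 × 10⁻¹² (69 min) to 3 × 10⁻⁸ (105 min), and 0.2% at an assumed 300 min. On the cited half-life nothing measurable should remain, so a quantifiable Week 12 pre-dose level would be direct evidence of carry-over, independent of infusion length. As an indication of sensitivity, Protocol 2.3.2 gives an earlier assay limit of 500 ng/mL and Cmax of 11,571 and 24,394 ng/mL at 5 and 9 mg/kg: 500/11,571 = 4.3% and 500/24,394 = 2.0%. The LLQ for this study is not given.

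**Step 4. Would dividing Cmax by the infusion rate (dose/Tinf) repair it?** No. That leaves 1 − exp(−kT), which still depends on T. For 2.5 h against 4 h the ratio becomes 1.368 × 150/240 = 0.86 (69 min) or 1.265 × 150/240 = 0.79 (105 min). The artefact changes sign and is not removed.

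**The case against.** The false-declaration rates need a net shift in infusion length across the cohort, and no document shows that one will occur. A reader might infer a systematic shift from sodium thiosulfate (STS), because with STS "the administration of SNF472 should be stopped 30 minutes before the end of the dialysis session to allow the STS infusion". The text does not support that. STS affects individual patients and could start or stop in either direction. Protocol 8.2.1 has the investigator confirm standard of care at Screening, so users may already be on it at Week 1. An infusion that already ends before the last 30 minutes needs no change. This objection stands: the rule can mislead, but it is not shown that it will.

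A reader might also infer that the zero replacement hides carry-over from the accumulation decision. It cannot under the present rule, because the pre-dose level is not part of it; only the descriptive summary is affected. The wording is also ambiguous: a Week 12 pre-dose sample comes before that day's dose but after many earlier ones, so it could fall under the set-to-missing sentence.

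Nor is 9.4.2 the only place where a problem could be seen. Infusion times and pre-dose levels are tabulated by visit and listed by subject, and SAP 9.4.1 permits case-by-case exclusions. That stands too, but the formal verdict would still follow the unadjusted rule.

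Finally, Protocol 2.3.2 reports PK results suggesting no accumulation in the earlier repeat-dose work, and no dosing or stopping decision hangs on this verdict. That limits the consequence but does not make the rule sound.

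**Conclusion.** The point holds, as a weakness in a decision rule rather than a demonstrated error in the result. Within the permitted range, infusion length alone can change Cmax by up to 1.27 to 1.37 times, assuming one-compartment kinetics and that the labelled-phytate half-life applies to SNF472 in these patients. With a net shift in length, the chance of a false declaration rises from the nominal 5% upward to anything from about 20% to over 90%, depending on the shift and the assumed CV. Without one, it stays near nominal. The lack of direction and the absence of the Week 12 pre-dose level from the rule are plain from the text and need no model. The zero replacement is a possible reading of SAP 9.4 that would bias the pre-dose summary. The correction is worth making because it is cheap, although the consequence for the trial is modest.

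**What to change.** **SAP 9.4.2.** Judge accumulation primarily on the Week 12 pre-dose concentration: the number and share of patients above the LLQ, with the individual values. Keep Cmax as support only. Analyse the Week 12/Week 1 ratio on the log scale, adjusted for the change in actual infusion time, for example with the log Tinf ratio as a covariate (the intercept is then the ratio at unchanged infusion time) or restricted to patients with similar Tinf at both visits. Do not simply divide by dose/Tinf. Count the Cmax ratio as pointing to accumulation only if the lower limit of its 90% CI is above 1.

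**SAP 9.4.** Set pre-dose values below the LLQ to 0, but leave a Week 12 pre-dose sample with no reportable value as missing, and state how many there are.

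**Cost.** SAP wording and slightly more analysis. Dose, Tinf and both pre-dose samples are already collected, and nothing changes in dosing or infusion practice. With about 15 patients the Tinf adjustment will be imprecise, which is a further reason to let the pre-dose level carry the conclusion.

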9.4.3 End of infusion PK concentration vs BWAT correlation

Correlation between End of Infusion PK Concentration vs Increase in BWAT Total Score from Week 1 to Week 12 will be assessed graphically by means of linear regression analysis where BWAT and EoI PK concentration will be considered as dependent and independent variables, respectively. Linear regression parameters, correlation estimate and their 95% confidence intervals will be presented.

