9.4.4 End of infusion PK concentration vs VAS correlation

Correlation between End of Infusion PK Concentration vs Increase in Pain Score (VAS) from Week 1 to Week 12 will be assessed graphically by means of linear regression analysis where VAS and EoI PK concentration will be considered as dependent and independent variables, respectively. Linear regression parameters, correlation estimate and their 95% confidence intervals will be presented.

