9.5 Pharmacodynamics

Plasma samples collected, at Week 1 and Week 12 pre and post-dose (around the Tmax for the post-dose measurement), from all subjects, will be used for exploratory pharmacodynamic (PD) assessment by using an in vitro test to assess the propensity for hydroxyapatite (HAP) crystal formation in plasma (see Protocol CT2015-04.2).

9.5.1 % PD Inhibition

The PD assessment will be performed by Laboratoris Sanifit and sent to [REDACTED] for analysis. The readout of the assay is a % inhibition of the propensity for hydroxyapatite crystal formation per each subject and visit.

The percent inhibition of HAP crystallization will be summarized by visit. In addition, the same information will be listed by all subjects and all timepoints together with the PK.

9.5.2 % PD Inhibition vs BWAT correlation

Correlation between % PD Inhibition vs Increase in BWAT Total Score from Week 1 to Week 12 will be assessed graphically by means of linear regression analysis where BWAT and % PD Inhibition will be considered as dependent and independent variables, respectively. Linear regression parameters, correlation estimate and their 95% confidence intervals will be presented.

9.5.3 % PD Inhibition vs VAS correlation

Correlation between % PD Inhibition vs Increase in Pain Score (VAS) from Week 1 to Week 12 will be assessed graphically by means of linear regression analysis where VAS and % PD Inhibition will be considered as dependent and independent variables, respectively. Linear regression parameters, correlation estimate and their 95% confidence intervals will be presented.

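### The four exposure-response regressions leave out the Week 1 score, which can cost precision and leaves the slope open to baseline confounding; a baseline-adjusted fit belongs beside the planned one, not in its place

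*SAP*

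**What the plan says.** SAP 9.4.3 states the outcome as a change score: "Correlation between End of Infusion PK Concentration vs Increase in BWAT Total Score from Week 1 to Week 12 will be assessed graphically". The model has one regressor: "BWAT and EoI PK concentration will be considered as dependent and independent variables, respectively". The output is fixed as follows: "Linear regression parameters, correlation estimate and their 95% confidence intervals will be presented".

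Three further sections have the same form:

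- 9.4.4: "VAS and EoI PK concentration will be considered as dependent and independent variables, respectively"
- 9.5.2: "BWAT and % PD Inhibition will be considered as dependent and independent variables, respectively"
- 9.5.3: "VAS and % PD Inhibition will be considered as dependent and independent variables, respectively"

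No supplied SAP text adds the Week 1 score. Section 8.3, despite covariates in its title, plans only subgroup summaries. Section 9.6 relates % inhibition to Cmax, not to lesion or pain. The SAP text between 8.4 and 8.6 and the table shells were not available, so a baseline term there cannot be excluded.

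The four sections also do not say whether Week 1 or Week 12 exposure is the regressor. Both are sampled.

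**The concern.** A change score usually depends on its starting value: high scores tend to fall and low ones to rise. Several features of this trial make that plausible. BWAT is bounded at 13 to 65 and VAS at 0 to 100 mm. Entry requires some pain or strong analgesics. The primary lesion is the largest one, and size is a scored BWAT item.

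Leaving the Week 1 score out can have two effects. Variation in change that baseline could explain stays in the residual and may widen the CI. If exposure is also related to baseline severity, the slope mixes the two, so regression to the mean can look like an exposure effect or hide one.

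The trial has no control arm, and these four regressions are the only planned analyses that link patient-level exposure to lesion or pain change. Readers will look to them for signs that the change tracks the drug.

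**Working it through.** **The plan's own figure.** The SAP gives no precision or power for these regressions. Its only design figure is 15 subjects for 80% power to show a healed rate above 25% when the truth is 60% (SAP 6.4). The exact binomial rule of at least 8 of 15 has one-sided alpha 0.0173 and power 78.7%, so 15 is reproduced to within 2 points. I use n = 15 below.

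**Inputs.** The model form is from SAP 9.4.3, 9.4.4, 9.5.2 and 9.5.3. The following are not in the documents and are assumed:

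- Week 1 and Week 12 SDs, equal and set to 1
- Week 1 to Week 12 correlation, rho, from 0.3 to 0.9
- exposure to Week 1 score correlation, g, from 0 to 0.5

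Exposure is standardised, so slopes are in baseline SDs per SD of exposure. Simulated figures use 40,000 trials per setting unless stated.

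**Step 1: precision when g = 0.** The residual variance of the change is 2(1 - rho) unadjusted and 1 - rho² adjusted, a ratio of (1 + rho)/2. In large samples the CI width is multiplied by the square root of that ratio: 0.81, 0.87, 0.92 and 0.97 at rho 0.3, 0.5, 0.7 and 0.9. At n = 15 the extra degree of freedom takes part of this back:

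| rho | Unadjusted mean CI width | Adjusted | Change |
|---|---|---|---|
| 0.3 | 1.415 | 1.198 | -15% |
| 0.5 | 1.199 | 1.092 | -9% |
| 0.7 | 0.927 | 0.898 | -3% |
| 0.8 | 0.757 | 0.753 | about 0 |
| 0.9 | 0.537 | 0.549 | +2% |

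With 10 analysable patients the gain is smaller: -12% at rho 0.3 (1.934 to 1.708), -5% at 0.5 (1.635 to 1.550), and +1% at 0.7 (1.261 to 1.274).

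**Step 2: systematic link, exposure related to Week 12 only through the observed Week 1 score.** Let b = rho × SD12/SD1. The bias of the unadjusted slope is (b - 1) × g × SD1. At rho 0.5 and g 0.3 this is (0.5 - 1) × 0.3 = -0.15. With a true slope of 0 the unadjusted 95% CI excludes 0 in these percentages of trials:

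| g | rho 0.3 | rho 0.5 | rho 0.7 |
|---|---|---|---|
| 0.3 | 9.6% | 7.9% | 7.1% |
| 0.5 | 19.2% | 14.8% | 10.4% |

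The adjusted fit stays near 5%. Masking also occurs: a true slope of -0.25 with rho 0.5 and g = -0.5 picks up a bias of (-0.5) × (-0.5) = +0.25 and is estimated as 0.00; the adjusted fit returns -0.25.

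**Step 3: systematic link, exposure tracking stable true severity.** Write each score as true severity plus independent visit noise. The change is then noise only, so it is unrelated to exposure and the unadjusted slope is unbiased. The adjusted slope has bias g(1 - rho)/(1 - g²). At g = 0.5 this is 0.35/0.75 = +0.47, 0.25/0.75 = +0.33 and 0.15/0.75 = +0.20 for rho 0.3, 0.5 and 0.7. The adjusted CI excludes 0 in about 34%, 22% and 13% of trials. At g = 0.3 the figures are about 12%, 9% and 7%, and a re-run agreed to within about one point. The unadjusted fit stays at about 5%.

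**Step 4: chance imbalance only.** With a population g of 0 and n = 15, the typical chance correlation is 1/√14 = 0.27. It exceeds 0.3 in size with probability 28% and 0.5 with probability 6%. The unadjusted test still rejects about 5% of the time overall. It also rejects about 4 to 5% of the time among trials whose chance correlation is near 0.27 (0.22 to 0.32).

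**Step 5: cost of adjustment when g = 0.5.** The CI widens by 2% at rho 0.3 (1.357 to 1.389), 9% at 0.5 (1.159 to 1.258), 14% at 0.7 (0.911 to 1.039) and 19% at 0.9 (0.534 to 0.634). If SD12 = 1.5 SD1 and rho = 0.67, then b = 1. There is no bias to remove, and the interval widens by 21% (1.341 to 1.623).

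**The case against.** A reader might infer that the planned slopes are biased by regression to the mean and that adjustment cures it. The documents do not support that. A systematic link between exposure and Week 1 severity is possible: dosing is by weight band, with a stated range of 5.6 to 9 mg/kg (Protocol 6.2), and infusion timing changes when STS is given (Protocol 8.2.3). No passage shows or excludes such a link. Nor does anything favour the mechanism in Step 2 over that in Step 3. Exposure is not randomised, so neither the change-score fit nor the adjusted fit is right in every case (Lord's paradox), and replacing one by the other could create a false signal. This objection stands.

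A reader might also infer that the chance correlation expected with 15 patients inflates the error rate. It does not (Step 4): the planned CI already allows for it. The rates of 7% to 19% need a systematic link.

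Nor is precision always lost. The gain from adjusting is largest when there is no bias to remove, and it shrinks or reverses as the exposure-baseline link grows.

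Finally, the consequence is limited. The SAP calls the study exploratory and a proof of concept. The regressions carry no threshold. The Protocol places the dose on the plateau of the PK/PD relationship, so exposure contrast may be small, which a covariate cannot mend. All of this bears on severity. None of it is a reason to withhold an adjusted fit that uses data already collected.

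**Conclusion.** The omission is present in all four regressions, in the text available. Its sure consequence is modest and conditional. If exposure is unrelated to the Week 1 score, the planned CI at n = 15 is wider than it need be when rho is below about 0.8; adjustment would narrow it by about 15%, 9% or 3% at rho 0.3, 0.5 or 0.7. If the two are systematically related, the planned slope may be biased in either direction, and so may the adjusted one, depending on a mechanism the documents do not settle. A single fit of either kind cannot separate exposure from baseline severity.

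All sizes rest on assumed correlations and SDs. Severity is low: no decision depends on these analyses, and the primary paired t-test is unaffected.

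**What to change.** In SAP 9.4.3, 9.4.4, 9.5.2 and 9.5.3:

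1. Keep the planned regression and plot.
2. Report beside it a fit that adds the Week 1 score of the dependent variable (BWAT total or VAS), with slope, partial correlation and 95% CIs.
3. Report the correlation between exposure and the Week 1 score. Within any sample, the unadjusted slope minus the adjusted slope equals the Week 1 coefficient of the adjusted fit times the slope of the Week 1 score on exposure, so this correlation shows how far the fits can diverge.
4. State that an exposure effect is read as supported only if the two fits agree, and that both are exploratory.
5. Name the visit whose exposure is the regressor.

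The cost is a few lines of SAP text and one degree of freedom in the added fit. If exposure and the Week 1 score are strongly correlated, the adjusted CI can be up to about 20% wider. No new data are needed.
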